Configurations for adjustable levels of restraint are: 1) no tie for a calm patient, 2) resistance tie (intermediate level of restraint) for a patient with flailing arms OR for resistance exercise as might be supervised by a physical therapist or nurse, and 3) rigid tie for temporary tighter restraint for an agitated or aggressive patient or as a temporary restraint during a procedure when the arm must be immobilized.

2. An evaluation in healthy subjects demonstrated that the first *Exersides*TM prototype was feasible to use and comfortable for subjects. The prototype was tested in 6 registered nurse (RN)

Figure 1. *Exersides*TM restraint prototypes in use.

A: Healthy volunteer able to move arm from the shoulder but the restrained hand is unable to self-extubate or remove the device. Adjustable levels of restraint possible using resistance or rigid (white) straps. **B:** The *Exersides*TM restraint (both arms) in use by an awake patient mechanically ventilated for acute lung injury and able to participate in care.

A

B

volunteers who, following consent, were videotaped and acted in both their staff role (bedside RN) and simulated patient role (performed in a hospital bed). In the patient role, volunteers were instructed to act as: 1) a calm and cooperative patient, 2) a confused patient with moving arms, and 3) an agitated patient. Results, summarized in Table 1, demonstrate high satisfaction.

3. A pilot study of first prototype *Exersides*TM restraint in ICU patients demonstrated feasibility and potential benefit. An IRB-approved pilot study was conducted in one Vermont hospital ICU, where 10 mechanically ventilated patients were alternately assigned to wear *Exersides*TM or traditional wrist restraints (n=5 in each group, 64±7 years old, 30% women). On day #3 of intubation, all patients were continuously videotaped for 4 consecutive hours while wearing their assigned device. All 5 patients in the *Exersides*TM group tolerated the device with no adverse events (defined as no self-extubation, feeding tube or IV dislodgement, self-removal of restraint, skin breakdown or bodily trauma to patient or nurse).

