 - **Outcomes/measures:** At least 90% of all outcomes planned for the RCT in Aim 3 (STTR Phase II) will be measured in the 8 patients: 1) actigraphy counts, 2) RASS sedation/agitation score,¹ 3) CAM-ICU delirium score,¹ 4) medication use, 5) satisfaction/acceptability/perceptions of novel restraint. Incidence of self-extubation will also be reported in addition to the following measures of efficacy: 1) patient-reported satisfaction measures including comfortable, safe, effective, preferable and more humane; and 2) staff-reported satisfaction measures including easy to don/doff, easy to change level, safe for staff, effective, preferable and more humane. See Aim 3 for these RCT measures.

- **Data collection/management, quality assurance & analysis:** See Aim 3.
- **Sample size:** N=8 was based on feasible enrollment from the single study site during the 9-month Phase I period (i.e., ~1 patient/month). Literature suggests that there is no advantage to including more than 6-10 subjects per group in a Phase I study, and most chemotherapeutic phase I studies have N=3 per cohort.¹ Thus, N=8 is adequate for the proposed Aims to prepare for the RCT in Aim 3.
- **Phase I Study follow-up.** The engineer will prepare a report on the outcomes of all assessments based upon STTR Phase I, and will decide (in consultation with the project leadership team) which device improvements/modifications will be required before use of device in Aim 3 (STTR Phase II).

PHASE II (3-site RCT to compare the novel restraint to traditional wrist restraints)

[figure not shown]
Aim 3: To conduct a multi-site, within-patient randomized crossover trial in older critically ill mechanically ventilated patients who require restraint, to compare the *Exersides™* restraint vs. traditional wrist restraints.

Overview and Study Design Phase II. The objective of the Phase II project is to conduct an RCT to measure 3 outcomes:

1. Mobility/activity evaluated by actigraphy (primary outcome)
2. Agitation, delirium, medication use (sedative, analgesic, and antipsychotic), and incidence of self-extubation (secondary outcomes)
3. Satisfaction with, and acceptability/perceptions of, the device by patient, family, and clinicians (secondary outcomes)

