To estimate the effect of the novel restraint, a linear model will be fit for the Log(total activity) as a function of main terms for treatment (Group A vs. B), time period (1pm-5pm vs. 9am-1pm), and treatment order (BA/AB vs. AB/BA). The natural logarithm is applied to the primary endpoint to reduce right skew in the distribution of total activity, with the exponentiated regression coefficient for the main term for treatment (A vs. B) in the linear regression model representing the relative difference in median total activity comparing the novel vs. traditional restraint, which will quantify the treatment effect. The linear model will be fit using weighted least squares to account for the correlation in the primary endpoint within a patient over time; the correlation structure will be specified as unstructured and allow for the possibility that the variance of the primary endpoint may be different in each period/day. The same linear models will be applied to the continuous secondary endpoints (e.g. medication dose). For the binary secondary endpoints, the effect of the novel vs. traditional restraint will be quantified using a longitudinal logistic regression model as a function of the same covariates (treatment, period, and treatment order). The longitudinal logistic regression model will be fit using generalized estimating equations allowing for an unstructured within-patient correlation structure. Activity, agitation, delirium and medication use will continue to be measured up to ICU discharge, death or Day 6. Starting on Day 3, the endpoints will be expressed as every 4-hour total activity counts, agitation assessment and total medication use, as well as every 12-hour delirium. With the data starting on Day 3, we will explore the long-term effects of the restraints by fitting linear and logistic longitudinal regression models that include main terms for treatment and time and the interaction of treatment and time. Time will be modeled as a restricted cubic spline with degrees of freedom selected by model fit statistics. As secondary outcomes are hypothesis-generating, we will not correct for multiple comparisons, but will consider the number of comparisons when interpreting results.

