Potential risks from the *Exersides*TM restraint device are very low. Our own preliminary data demonstrate safety in that no adverse or severe adverse events (i.e. no self-removal of endotracheal tubes, feeding tubes, intravenous lines, etc.) – these preliminary data are from a pilot study that has already taken place that enrolled critically ill patients in a single intensive care unit. Although self-removal of tubes and lines is a risk, as occurs with any existing currently available restraint device, we anticipate that this risk is very low due to the design of the *Exersides*TM restraint that intentionally was created to further reduce this risk in comparison to traditional restraints. Other potential risks include skin breakdown from the *Exersides*TM restraint device, and a theoretical increased risk of increased removal of upper extremity peripheral IVs, but we did not observe any of these events in our pilot study.

There are few alternative treatments to participating in this RCT. Use of the *Exersides*TM restraint device is not standard of ICU care at any clinical center. However, this study will not alter clinical care that occurs with regard to other aspects of critical illness. Specifically, only patients whose physicians have already written an order requiring physical restraints will be considered for the study. The novel *Exersides*TM restraint device will only be used while such an order is active, as part of routine clinical care (i.e. no patient will receive the *Exersides*TM restraint device without a need for physical restraint as documented/ordered by the ICU clinicians). All study sites currently follow (and will continue to follow throughout the duration of the study) Joint Commission requirements for re-assessment and re-ordering restraints at least once every 24 hours. If a restraint is no longer required/ordered as part of routine clinical care, then use of the *Exersides*TM restraint device will immediately stop and not re-start unless a renewal of a restraint order is done, as required by clinical circumstances. In no way will the study have any influence over the ordering of restraints as part of clinical care in the ICU.

ADEQUACY OF PROTECTION AGAINST RISKS

Recruitment and Informed Consent

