The novel restraint device being tested in the FREEDOM Trial is considered so low-risk that it is exempt

from FDA IDE regulations. Nevertheless, participants will be monitored for medical events of interest including skin laceration, upper extremity joint pain, and equipment damage that may not be serious but may be related to the novel restraint intervention. These data will be collected daily while the subject is on study (through day 3 for the pilot study and day 7 for the RCT). These data will be recorded in the electronic database.

2. *Adverse Event (AE) Reporting*

Given the high acuity of diseases and morbidity related to critical illness in the patient population under study (over age 60 years old receiving invasive or non-invasive mechanical ventilation and requiring restraint), it is difficult to identify an adverse event (AE) within the constellation of symptoms related to the normal evolution of critical illness. Therefore, expected AEs (e.g. abnormal laboratory values, aberrant physiology such as fever or tachycardia or hypotension, etc.) consistent with the underlying pathophysiology or progression of underlying illness will neither be collected nor reported. Only AEs that are both unexpected and felt to be related (to any degree) to the novel restraint device will be collected and reported, the majority of which will be considered “events of interest” as above. The investigator will use his/her judgment to determine whether an AE is considered to be definitely related, probably related, possibly related, unlikely related, or not related (see table below in 5.a.). These unexpected and related (to any degree) AEs will be documented in the participant medical record and/or study file. It is the responsibility of the investigator to review all documentation (e.g. hospital progress notes, laboratory results, diagnostic reports, etc.) regarding each event. This reporting process is outlined below.

3. *Serious Adverse Event (SAE) Reporting*

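### Non-serious feeding-tube and IV-line removals are not collected under wrist restraint and only selectively under the novel device, so removal cannot be compared between devices

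*Combined protocol and SAP*

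**What the plan says.** **Adverse event rule** (Adverse Event and Unanticipated Problem Reporting, item 2): "Only AEs that are both unexpected and felt to be related (to any degree) to the novel restraint device will be collected and reported". No matching rule covers wrist restraint.

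**Events of interest** (item 1): daily monitoring covers "medical events of interest including skin laceration, upper extremity joint pain, and equipment damage". The list is open-ended, but its scope is events such as "equipment damage that may not be serious but may be related to the novel restraint intervention". Tube and line removal is not named.

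**Serious events** (item 3): unexpected SAEs are collected whichever device is worn.

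**The risk as the protocol describes it** (Potential Risks, repeated in the device risk assessment): "Although self-removal of tubes and lines is a risk, as occurs with any existing currently available restraint device", together with "a theoretical increased risk of increased removal of upper extremity peripheral IVs" for the novel device. The earlier pilot (Preliminary Studies and Data, item 3) defined freedom from adverse events as "no self-extubation, feeding tube or IV dislodgement, self-removal of restraint, skin breakdown or bodily trauma to patient or nurse".

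**Self-extubation**: the Phase II overview lists it among the outcomes, as "Agitation, delirium, medication use (sedative, analgesic, and antipsychotic), and incidence of self-extubation (secondary outcomes". It does not reappear in Table 7, in the Outcome 2 text, or in the endpoints of the Statistical Analysis Plan, which says "Activity, agitation, delirium and medication use will continue to be measured up to ICU discharge, death or Day 6".

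**The concern.** The device is meant to free the arm while still keeping the hand away from tubes and lines. Mobility is measured carefully under both devices. The matching safety question, whether freer arms lead to more removals, needs a count under both devices, and the collection rule does not supply one for non-serious events.

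Without a wrist-restraint count, the DSMB at its scheduled review (27 patients completed) and the readers of the final report have no background to set novel-device removals against. The novel-device count also passes through two investigator judgements, so a low count could mean few removals or few removals judged reportable. Feeding-tube and peripheral IV removals are mostly non-serious, so the SAE route would miss most of them. They include the one event for which the protocol itself raises a possible increase.

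**Working it through.** The plan states no figure on this point, so there is none to reproduce. The check sets the collection rules side by side and then works out the exposure from the schedule.

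**Step 1. What route collects each event?**

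| Event | Under wrist restraint | Under the novel device |
|---|---|---|
| Serious, unexpected removal | Collected as an SAE | Collected as an SAE |
| Non-serious feeding-tube or IV-line removal | No route | Only if judged unexpected and related to the novel device |
| Self-extubation | Declared outcome; no source, timing or attribution rule | Same |

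The middle row is the gap. The two judgements on the novel side are not equally strict. The relatedness test is lenient, because Reporting Timelines counts an event rated unlikely related as related. The expectedness test is less clear. Item 2 describes expected events as those consistent with the underlying illness, but Potential Risks names self-removal as a known risk, so investigators could reasonably differ.

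**Step 2. How much restraint time falls under wrist restraint?** Inputs are from Implementation of the RCT intervention. Take one patient randomized to each starting device, and let D be the hours worn on Days 3-6, assumed equal in the two.

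- Sessions on Days 1-2: 2 patients x 2 days x 4 h = 16 h on each device.
- Days 3-6: D hours on each device.
- Two wrist-only nights, 5pm to 9am: 2 patients x 2 nights x 16 h = 64 h, all wrist.
- Wrist share = (16 + D + 64) / (2 x (16 + D) + 64).

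| D | Novel hours | Wrist hours | Wrist share |
|---|---|---|---|
| 96 (all of Days 3-6) | 112 | 176 | 176/288 = 61% |
| 48 | 64 | 128 | 128/192 = 67% |
| 0 (restraint ends at Day 3) | 16 | 80 | 80/96 = 83% |

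With the two nights left out, the share is 50% for any D. At equal hourly risk these are also the shares of removals that fall under wrist restraint. The non-serious feeding-tube and line removals among them go uncollected. Hours worn are only a proxy for time at risk. Patients on non-invasive ventilation have no endotracheal tube, and tubes and lines are taken out clinically while restraint continues.

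**Step 3. Can the pilot fill the gap?** It reports no removals in 5 patients x 4 h = 20 novel-device hours. With a constant rate, the one-sided 95% upper bound is -ln(0.05)/20 = 0.150 per hour, or 150 per 1000 h. It gives no removal count for the wrist group. It therefore neither excludes an excess nor supplies a background rate.

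**Step 4. What kind of comparison would the data support?** At D = 96, Days 3-6 supply 96 of the 112 non-night hours on each device (86%), and in those hours each patient wears one device. Most of the comparison is therefore between patients, and repeated removals by the same patient would make a simple Poisson interval too narrow.

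**The case against.** The strongest case on the other side has four parts.

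- **Serious removals are covered.** An unexpected removal that jeopardises the patient can qualify as an important medical event and is collected under either device. This stands, and it limits the gap to non-serious events.
- **Self-extubation is already an outcome.** The adverse event rule does not govern a declared secondary outcome. The analysis plan has a model for binary secondary endpoints, and the device worn could be worked out from the schedule and the daily compliance item in Table 6 once an event is timed. This stands too. A reader might infer from Table 7 that self-extubation has been dropped; the documents do not support that. What is missing is source, timing and a rule for assigning the event to a device.
- **The DSMB can close the gap.** It approves the plan for identifying adverse events and can request more data. That plan and the charter are not in the documents and might add removals. But the protocol's rule is exclusive as written, and data requested later would have to be rebuilt from charts.
- **Sessions are observed and filmed.** Some wrist-restraint removals may be seen. The stated use of the video is to tell purposeful from agitated movement; nothing says removals will be coded, and nights are not recorded.

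A reader might also infer that removals will be fully counted on the novel device and not on the other, so that the adverse event table must be biased against the novel device. The documents do not support this. Capture on the novel side is insecure as well, because an event must be unexpected as well as related. Bias is possible in either direction but is not shown.

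**Conclusion.** The point holds for non-serious feeding-tube and IV-line removals. As written, they are not collected under wrist restraint and are collected under the novel device only after two judgements, so the trial cannot compare a risk that the protocol itself names. For self-extubation the gap is smaller: the intent to measure it is stated, the method is not.

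The conclusion follows from the wording of the collection rule and needs no assumed event rate. Its size in events cannot be given, because the documents contain no background rate. The exposure shares of 61% to 83% (50% without the wrist-only nights) rest on continuous wear as scheduled, equal Days 3-6 wear in the two groups, and hours worn as a stand-in for time at risk. The primary outcome is unaffected. The change should be made before the RCT enrolls, since removals not recorded at the time may not be recoverable.

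**What to change.** 1. In Events of Interest, add self-extubation and self-removal of any feeding tube or line. Take them daily from the chart for Days 1-6, nights included, under both devices and regardless of judged relatedness or expectedness. Record the time of the event, the device worn, and the hours each device was worn while the tube or line was in place.
2. Add self-extubation to Table 7 with the same source and timing, among patients with an endotracheal tube.
3. Report counts and rates by device, under coded labels in keeping with the DSMB masking rule, at the review after 27 patients and in the final report. Show the two wrist-only nights separately; the remaining hours are then balanced if Days 3-6 wear is similar, which also helps protect the code. Treat the results as descriptive estimates, with intervals that allow for clustering within patient, and not as a formal test.

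The cost is one short form item plus chart abstraction on up to 6 x 54 = 324 patient-days, or 6 x 60 = 360 if enrollment is extended to replace missing data. Daily events-of-interest collection and the compliance item already exist, and no new meeting or unmasking is needed. Overnight events depend on nursing notes, so some will be missed.
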